8.1.6 Sensitivity to (other) covariates

Efficacy endpoint analysis, as described in [section 8.1.2](#), was repeated for subjects in the ITT

- without adjusting for age group
- using country as covariate,
- using baseline cow's milk specific sIgE (categorized as in [section 7.1.2](#)) as covariate
- using filaggrin mutation subgroup (With/Without filaggrin mutation) as covariate
- using recruitment part (Part A/Part B)

These analyses were performed without adjusting for age group due to small sample sizes expected.

8.1.7 Subgroup analyses

Efficacy endpoint analysis, as described in [sections 8.1.2](#), (and [8.1.3](#) for age subgroups only), were repeated for subjects in the ITT for the following subgroups:

This document is confidential

Statistical Analysis Plan

- each age groups (age group was not included as covariate; Newcombe confidence interval was not stratified on age group)
- each country (no covariate)
- baseline cow's milk specific IgE (categorized as in [section 7.1.2](#)) (no covariate)
- each filaggrin mutation subgroup (With/Without filaggrin mutation) (no covariate)

For descriptive purposes, 90%-CI were provided for the treatment comparisons.

8.2 SECONDARY EFFICACY ENDPOINTS AND ANALYSES

ITT, OLS-500 or OLS-300 (if applicable) will be employed for secondary efficacy analyses. Observed data will be used, no imputation of missing data will be performed.

8.2.1 Treatment Responders

8.2.1.1 OL-500 Analysis

The number and percentage (%) of subjects who were treatment responders or non-responders at Month 24 were summarized overall and in each age-group, in total and by initial randomized treatment group (placebo/dose level/overall active), if applicable.

Response status at each time point (Months 12, 24, 36, 48 if applicable) were listed for subjects with at least one DBPCFC performed during Viaskin Milk 500 μ g open-label treatment period.

8.2.1.2 OL-300 Analyses

Optional food challenge can be performed after 12 months and/or 24 months of open-label treatment with Viaskin Milk 300 μ g. No DBPCFC was performed at the end of 500 μ g period (prior to switch to open-label treatment with Viaskin Milk 300 μ g).

A responder in the OL-300 analyses is defined as a subject who meets at least one of the following criteria:

- A \geq 10-fold increase in the cow's milk proteins CRD at the Month 12 DBPCFC (VS3/VS4) [Month 24 (VS6/VS7)] after switch to Viaskin Milk 300 μ g as compared to baseline value and reaching at least 144 mg of cow's milk proteins
- A CRD of cow's milk proteins \geq 1444 mg at the Month 12 DBPCFC (VS3/VS4) [Month 24 DBPCFC (VS6/VS7)] after switch to Viaskin Milk 300 μ g

Two types of analyses will be performed, considering different timepoints as baseline:

1. Considering the CRD determined by screening DBPCFC as baseline CRD.
2. Considering the CRD determined by the DBPCFC which was conducted prior to the subject receiving any active treatment as baseline CRD. This refers to Month 12 DBPCFC for subjects randomized to the placebo treatment arm and to screening DBPCFC for subjects randomized to any active treatment arm.

This document is confidential

Statistical Analysis Plan

Both types of responders will be summarized overall and in each age-group, in total and by initial randomized treatment group (placebo/dose level/overall active) in the OLS-300.

For the calculation of rates and percentages, only the subjects with DBPCFC at the respective baseline and at Month 12 (VS3/VS4) [Month 24 (VS6/VS7)] after switch will be used.

8.2.2 Cumulative Reactive Dose (CRD) of Cow's Milk Proteins at Months 12 to 48

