7.3.1.1.1 DBPCFC at Screening (Visits 2 and 3)

During the screening DBPCFC, the doses of cow's milk proteins to be ingested will be 1 mg, 3 mg, 10 mg, 30 mg, 100 mg, and 300 mg administered at 20-minute intervals. The Investigator may use clinical judgment to increase the intervals between doses in case there is a suspicion that an objective reaction may be developing (see [Section 7.3.1.1.3](#)). Very occasionally, the Investigator may use clinical judgment to repeat the same dose (but only once) before administration of the next higher dose and only if there is a suspicion that an objective reaction may be developing (see [Section 7.3.1.1.3](#)). The dose and the time of administration of each dose (and of a repeated dose when applicable) will be recorded in the eCRF. The subjects will be kept under observation for an additional 3 hours after the ingestion of the last dose of the challenge formula.

The subjects must react objectively (see [Section 7.3.1.1.3](#)) at or below the eliciting dose of 300 mg of cow's milk proteins to be eligible for randomization to treatment. Hence, this screening DBPCFC will be stopped at or below the dose of 300 mg on either day of the challenge (milk or placebo), whether reactions have occurred or not. Subjects who have not reacted objectively at or below the eliciting dose of 300 mg of cow's milk proteins will be considered ineligible for this study.

All subjects should undergo procedures of the DBPCFC on both days. However, in exceptional cases, the DBPCFC on the second day of the challenge might not be performed if the subject had a severe anaphylactic reaction during the first day of the challenge, leaving no doubt about the nature of the formula administered, ie, cow's milk. In this rare case and in this case only, the food challenge formula will be unblinded to confirm that the subject effectively received the milk formula. A severe anaphylactic reaction would involve a >20% drop of blood pressure, cyanosis or SpO₂<92%, confusion, collapse, loss of consciousness, 3 doses of epinephrine or more (see [Appendix 14.4](#)).

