All DBPCFCs at Month 12 and forward will be conducted using the same procedures that are described for the screening DBPCFC, with the exception that the dosing will continue beyond the 300 mg dose of cow's milk proteins if there are no objective symptoms (see [Section 7.3.1.1.3](#)) at the 300 mg dose. The challenge must be continued up to the last dose of 3000 mg of cow's milk proteins or until an objective reaction occurs (as defined in [Section 7.3.1.1.3](#)).

For all DBPCFCs at Month 12 and forward, the doses of cow's milk proteins will be 1 mg, 3 mg, 10 mg, 30 mg, 100 mg, 300 mg, 1000 mg, 2000 mg, and 3000 mg administered at 20-minute intervals. The Investigator may use clinical judgment to increase the intervals between doses in case there is a suspicion that an objective reaction may be developing (see [Section 7.3.1.1.3](#)). Very occasionally, the Investigator may use clinical judgment to repeat the same dose (only once) before administration of the next higher dose and only if there is a suspicion that an objective reaction may be developing (see [Section 7.3.1.1.3](#)). The dose and time of administration of each dose (and of a repeated dose when applicable) will be recorded in the eCRF. The subjects

will be kept under observation for an additional 3 hours after the ingestion of the last dose of the challenge formula.

Subjects should undergo both days of the DBPCFC (milk and placebo). However, in exceptional cases, the DBPCFC on the second day of the challenge might not be performed if the subject had a severe anaphylactic reaction during the first day of the challenge, leaving no doubt about the nature of the formula administered, ie, cow's milk. In this rare case and in this case only, the formula will be unblinded to confirm that the subject effectively received the milk formula. A severe anaphylactic reaction would involve a >20% drop of blood pressure, cyanosis or SpO₂<92%, confusion, collapse, loss of consciousness, 3 doses of epinephrine or more (see [Appendix 14.4](#)).

At the end of the second day of the food challenge, the sequence of the 2 formulas (milk or placebo) administered will be unblinded by the appropriate unblinded staff (eg, dieticians, study nurses, pharmacists, pharmacy technicians, licensed medical assistants, or any other qualified site personnel, as delegated by the Investigator) and revealed to the medical staff. The results of the challenge will then be established and recorded in the eCRF.

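### In the second OL-300 responder analysis, criterion 2 ignores the Month 12 baseline, so an ex-placebo subject already at 1444 mg or more before active treatment counts as a responder without any rise

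*SAP*

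**What the plan says.** SAP 8.2.1.2 sets the rule: "A responder in the OL-300 analyses is defined as a subject who meets at least one of the following criteria". Criterion 1 is a 10-fold or greater increase in CRD "as compared to baseline value and reaching at least 144 mg of cow's milk proteins". Criterion 2 is a CRD of at least "1444 mg at the Month 12 DBPCFC (VS3/VS4) [Month 24 DBPCFC (VS6/VS7)] after switch". Only criterion 1 mentions a baseline.

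The same rule is applied with two baselines. The first is the screening challenge for everyone. The second is the last challenge before active treatment. For active-randomised subjects this is still screening; for the others, "This refers to Month 12 DBPCFC for subjects randomized to the placebo treatment arm".

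Rates are shown by initial randomised group and in total. The denominator is the subjects with a challenge at the relevant baseline and after the switch. Nothing removes a subject whose baseline is already at the threshold. The OLS-300 definition (SAP 5.6) and the switch criteria (Protocol 4.4) do not remove such a subject either.

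The two kinds of baseline challenge have different ceilings. Protocol 7.3.1.1.1 states that "this screening DBPCFC will be stopped at or below the dose of 300 mg". For Month 12 onwards, Protocol 7.3.1.1.2 states: "The challenge must be continued up to the last dose of 3000 mg of cow's milk proteins or until an objective reaction occurs".

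**The concern.** The absolute threshold is safe when baseline is screening. Entry requires a reaction by the 300 mg dose, so any later CRD of 1444 mg or more is a rise. The Month 12 challenge has no such cap. A placebo subject can reach 1444 mg or more at Month 12, whether through natural course or challenge variability, before receiving any active patch. The second analysis would then call that subject a responder relative to the very challenge at which the threshold was reached.

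Active-randomised subjects keep the screening baseline and cannot be classified this way. The ex-placebo column can therefore contain responders with no improvement over their stated baseline, while the other columns of the table cannot. A reader of the ex-placebo rate would naturally take it as change since the start of active treatment.

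**Working it through.** **Inputs**
- Screening doses: "1 mg, 3 mg, 10 mg, 30 mg, 100 mg, and 300 mg administered at 20-minute intervals" (Protocol 7.3.1.1.1).
- Doses from Month 12 onwards: the same six, then 1000, 2000 and 3000 mg (Protocol 7.3.1.1.2).
- CRD: the sum of all doses given, repeats included (SAP 4.1). Each dose may be repeated once.
- Randomised: 18 in Part A and 180 in Part B (SAP 3.1), at 2:1 and 1:1:1:1 (SAP 3.4).

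**The plan's own figure.** 1 + 3 + 10 + 30 + 100 + 300 + 1000 = 1444 mg. At 300 mg per 9.4 mL this is 1444 × 9.4 / 300 = 45.2 mL, which matches the stated 45 mL. The protocol synopsis prints 144 mg beside 45 mL for criterion 2. Protocol 8.1.6.1 and SAP 4.1 print 1444 mg, and the arithmetic supports 1444 mg.

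**Cumulative ladder.** 1, 4, 14, 44, 144, 444, 1444, 3444, 6444 mg.

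**Screening baseline.** The maximum is 444 mg, or 2 × 444 = 888 mg with every dose repeated. Criterion 2 then implies at least a 1444 / 444 = 3.25-fold rise, or 1444 / 888 = 1.63-fold with all repeats. No ladder pair with a later CRD at or below baseline is a responder.

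**Month 12 baseline of 1444 mg or more.** Criterion 1 needs at least 10 × 1444 = 14,440 mg. The ladder gives 6444 mg, or 2 × 6444 = 12,888 mg with every dose repeated. Criterion 1 is out of reach, so criterion 2 alone decides:

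| Month 12 CRD (mg) | CRD after switch (mg) | Direction | Classified as |
|---|---|---|---|
| 1444 | 1444 | unchanged | responder |
| 3444 | 3444 | unchanged | responder |
| 6444 | 6444 | unchanged | responder |
| 3444 | 1444 | fall | responder |
| 6444 | 1444 | fall | responder |
| 6444 | 3444 | fall | responder |
| 1444 | 444 | fall | non-responder |
| 3444 | 444 | fall | non-responder |

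The first six rows are all the ladder pairs in which a subject is a responder without a rise.

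**How many subjects.** Part A placebo is 3 × 2 = 6. Part B placebo is about 180 / 4 = 45, assuming equal allocation. That gives about 51 in all. The documents do not state what share had a Month 12 CRD of 1444 mg or more. As an assumed range, 0%, 5%, 10% and 20% of 51 give 0, 2.6, 5.1 and 10.2 subjects, if all switched and were re-challenged. Among those re-challenged, a share p who were at or above 1444 mg at Month 12 and stayed there adds 100 × p percentage points to the ex-placebo rate with no rise. A smaller number of challenges lowers the count but not necessarily the percentage.

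**The case against.** The strongest reply is that little rests on this analysis. Protocol 8.1.6.2.1 says responders after Month 12 will only be explored, and SAP 8.2.1.2 plans summaries without a test. Keeping the primary endpoint's absolute threshold gives continuity of definition. The SAP does not say that the second baseline is meant to isolate the effect of active treatment. The origin columns also differ by a year of active exposure, so this rule is not the only reason they are not alike. All of this stands, and it limits the weight of the point.

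SAP 8.2.2.2 also plans CRD values, changes, and counts of improved, stable and deteriorated subjects against the same baseline. Unchanged subjects would appear there as stable. That helps, but it does not alter responder status. The printed definition of deterioration also uses the same greater-than sign as improvement, so as written that count does not separate falls.

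Numbers may be small. The post-switch challenge is optional, and the switch requires consent and adequate compliance. Protocol 3.1.4 notes that early re-introduction of milk may suit some subjects, so the most tolerant may be the least likely to be re-challenged. This is fair, and zero cases is possible.

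Excluding these subjects from the denominator would also thin only the ex-placebo column, and would drop a genuine rise from 1444 to 6444 mg. That is a reason to report the rate both ways.

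**Conclusion.** The point holds on the text. With the pre-active baseline, criterion 2 classifies ex-placebo subjects without reference to that baseline. Those at 1444 mg or more at Month 12 are responders if unchanged. Those above 1444 mg are responders after a fall that leaves them at or above 1444 mg. It should be fixed, but it is not a critical fault: it touches the ex-placebo column, and totals containing it, in one of two descriptive analyses.

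A reader might infer more than the documents support:
- **That the primary result is affected.** It is not; the Month 12 primary analysis uses the screening baseline.
- **That any fall counts as response.** A subject at exactly 1444 mg who falls is a non-responder, as is one who goes from 3444 to 444 mg.
- **That criterion 1 fails from any baseline above 6444 / 10 = 644.4 mg.** That ignores permitted repeat doses. The safe statement is for baselines of 1444 mg or more.
- **That the ex-placebo rate is inflated by a known amount.** No placebo CRD distribution is given. About 51 subjects is an upper bound that assumes equal Part B allocation, and the percentages in the working are assumptions. The rule could inflate the rate; the documents do not show that it does.

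**What to change.** In SAP 8.2.1.2, for the second analysis only, make criterion 2 require a CRD below 1444 mg at the baseline in use as well as a post-switch CRD of at least 1444 mg. Show subjects at or above 1444 mg before active treatment in a separate row with their CRD change, so that real rises among them remain visible. Give the responder rate twice: with these subjects in the denominator as non-responders, and without them. Leave the screening-baseline analysis unchanged.

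This removes all six no-rise pairs. It does not deal with a small rise to 1444 mg from a baseline just below it after a partial last dose; the CRD change summaries in SAP 8.2.2.2 would show such a case.

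The cost is one sentence in the SAP, one table row and a second rate. Protocol 8.1.6.2.1 leaves the details to the SAP, so no protocol change is needed. SAP 11.1 says the Month 12 data were locked and unblinded, so the sponsor can count the affected subjects directly. For the same reason, the change should be dated and recorded as made after those data were known.

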8.2.2.1 Double-blind Month 12 and OL-500 analyses

The actual value and changes from baseline of CRD of Cow's milk proteins was summarized overall and for each age group, in total and by (initial randomized) treatment group (placebo/dose level/overall active), at each time point until Month 12 on the ITT for the randomized blinded treatment period. This analysis was repeated until Month 48 (if applicable) for the Viaskin Milk 500 μ g open-label treatment period on the OLS-500 and on PPS-500. Change from Month 12 to each timepoint was also tabulated for the OL-500 period.

An ANCOVA model was built to compare the mean value in \log_{10} -transformed CRD at Month 12 between each dose level group and placebo for subjects in the ITT. Treatment group, age group, and baseline \log_{10} -transformed CRD were included in the model. The adjusted Least Squares Mean (LS-Mean) differences versus placebo were reported together with associated 95% confidence intervals and corresponding p-values. A SAS code similar to the following was be used.

```
PROC MIXED DATA =<indata>;
  CLASS agegroup treat;
  MODEL aval = base agegroup treat / DDFM=kr;
  LSMEANS treat/cl diff;
RUN;
```

In addition to the analysis of the \log_{10} -transformed data, a sensitivity analysis was performed using an appropriate non-parametric test procedure. The treatment effect was estimated using Hodges-Lehmann estimate of the difference in medians of CRD change from month 0. The corresponding 95% confidence interval and the p-value from the hypothesis test of no difference between the treatment groups (Wilcoxon rank-sum test) stratified on age group were presented.

The ANCOVA model and its sensitivity analysis will not be repeated for open-label time points.

Note that only the active milk food challenge will be included, placebo food challenges will not be included.

This document is confidential

Statistical Analysis Plan

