Subjects from both Part A and Part B were randomized to receive treatment with Viaskin Milk or placebo for 12 months (randomized double-blind treatment period), after which a second DBPCFC was performed. The primary analysis of this study was conducted after data have been collected up to Month 12 visits including both days of the DBPCFC at Month 12. Consequently, results from the safety and efficacy data collected in all Part A and Part B subjects up to and including the Month 12 visits were reported in the 12-Month Clinical Study Report (CSR).

This document is confidential

Statistical Analysis Plan

After the Month 12 DBPCFC, all subjects from Part A and Part B were to continue treatment with active Viaskin Milk 500 μ g, the highest dose determined to be safe, for up to a maximum of 36 months (DBPCFCs at Month 24, 36 and 48). Following results of the 12-month blinded period, all eligible subjects who wish to continue participation in the study switched from Viaskin Milk 500 μ g to Viaskin Milk 300 μ g for 24 additional months of treatment, as per protocol Amendment 5, independently of the duration of previous treatment (Optional DBPCFC at 12 and/or 24 months after switch to Viaskin Milk 300 μ g dose).

A final End-of-Study (EOS) visit will be performed for all subjects when they completed or stopped the study. The EOS visit was to take place 2 weeks after the last DBPCFC at Month 24 for the subjects completing the study at Month 24, or 2 weeks after the last DBPCFC at Month 48, for subjects completing the study extension at Month 48. For subjects switching to Viaskin Milk 300 μ g, the EOS visit will take place 2 weeks after the end of the 24-month treatment period at this dose.

Three-hundred-and-eight children and adolescent subjects have been screened, 198 were randomized in this study, 18 subjects in Part A and 180 subjects in Part B. In Part B, the randomization was stratified by site and by age group (children 2 to 11 years old at the time of Visit 1; adolescents 12 to 17 years old at the time of Visit 1).

The total duration of the study will be approximately 6 years and the total duration of participation in the study will differ for each individual subject and could be up to approximately 6 years.

[Figure 1](#) of the study protocol version 6.0 presents a summary of the enrolment process into Part A and Part B of the study, and [Figures 2](#) and [3](#) present the overview of the study design.

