6.1.3 Presentation of Statistical Tests

Unless otherwise stated, all formal tests of hypotheses will be conducted at the two-sided level of significance with alpha=0.05.

Any calculated p-values will be rounded to 3 decimal places; p-values less than 0.001 will be presented as 'p < 0.001' and p-values greater than 0.999 will be presented as 'p > 0.999'.

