8.2.2.2 OL-300 Analyses

Descriptive summaries will be presented overall and in each age-group, in total and by initial randomized treatment group (placebo/dose level/overall active) in the OLS-300, using different definitions of baseline values, as described in [Section 8.2.1.2](#)

1. Considering the CRD determined by screening DBPCFC as baseline CRD.
2. Considering the CRD determined by the DBPCFC which was conducted prior to the subject receiving any active treatment as baseline CRD.

The absolute CRD values at each timepoint will be presented, in addition with the change from screening and from last value prior any active treatment, taking the different types of baseline into account.

In addition the number (%) of subjects with CRD improvement / stable / deterioration from screening DBPCFC and from last DBPCFC prior any active treatment at each timepoint will be presented, using the following definitions:

- Improvement: CRD at timepoint > CRD at baseline
- Stable: CRD at timepoint = CRD at baseline
- Deterioration: CRD at timepoint > CRD at baseline

with baseline denoting screening DBPCFC or last DBPCFC prior any active treatment, respectively.

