12.4 AMENDMENT 4: FINAL VERSION 4.0, 18 DECEMBER 2017

Following changes from analyses scheduled in protocol amendment 4, dated 18 December 2017 have been implemented in this Statistical Analysis Plan (version 3.0):

- a) *In order to homogenize analyses strategy with DBV Technologies' other statistical analysis plans, early termination assessments will be analyzed as having occurred at the next scheduled assessment.*
- b) *Visit time windows have been defined for the main visits occurring during the randomized blinded treatment period. Number and percentage of subjects respecting the time window defined in Table 3 will be provided.*
- c) *Clarification has been provided in case of several filaggrin mutations presented by subject in order to define the subject's homozygous/heterozygous status.*
- d) *In order to homogenize analyses strategy with DBV Technologies' other statistical analysis plans, sensitivity analysis on primary endpoint presenting relative risks has been removed and replaced by presenting difference of responder rate and its Newcombe 95% confidence interval stratified on age group.*
- e) *Sensitivity analyses on primary endpoint have been added:*
 - *On missing data handling: analysis using observed data, analysis of best case scenario and of worst case scenario*
 - *On covariates: analyses adjusted on recruitment part of the study (Part A / Part B)*
- f) *Sensitivity analyses on cumulative reactive dose using an appropriate non-parametric test procedure. The treatment effect will be estimated using Hodges-Lehmann estimate of the difference in medians of CRD change from month 0. The corresponding 95% confidence interval and the p-value from the hypothesis test of no difference between the treatment groups (Wilcoxon rank-sum test) stratified on age group will be presented.*
- g) *In order to comply with requests from FDA on another project, serious adverse events occurring during DBPCFC will not be considered for adverse events analyses; they will be described separately.*

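### The non-parametric check on Month 12 CRD is on untransformed milligram change without baseline adjustment, so its Hodges-Lehmann estimate depends on the baseline dose mix and cannot be compared with the log10 ANCOVA it accompanies

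*SAP*

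**What the plan says.** SAP 8.2.2.1 gives two between-arm comparisons of Month 12 CRD in the ITT set.

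- **Main model.** An ANCOVA on log10 CRD with treatment, age group and log10 baseline CRD, coded as "MODEL aval = base agegroup treat / DDFM=kr". It reports adjusted mean differences from placebo with 95% confidence intervals.
- **Sensitivity analysis.** Presented as an addition to the log10 analysis, "a sensitivity analysis was performed using an appropriate non-parametric test procedure", and "The treatment effect was estimated using Hodges-Lehmann estimate of the difference in medians of CRD change from month 0". The p-value is from a Wilcoxon rank-sum test stratified on age group. Neither a transformation nor baseline CRD is mentioned.

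SAP 4.1 defines CRD as a sum of doses in milligrams. An untransformed change is therefore in milligrams, and the contrast with the log10 analysis supports that reading. The change log in SAP 12.4(f) uses matching words: "The treatment effect will be estimated using Hodges-Lehmann estimate of the difference in medians of CRD change from month 0".

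For the open-label 300 µg period, SAP 8.2.2.2 states: "The absolute CRD values at each timepoint will be presented, in addition with the change from screening and from last value prior any active treatment".

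**The concern.** A sensitivity analysis is most useful when it relaxes one assumption and leaves the rest alone. Here three things change together: the normality assumption, the scale of the effect and the adjustment for baseline CRD. If the result differs from the ANCOVA, the difference cannot be put down to non-normality.

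The estimate is also hard to carry elsewhere. Ranks of a difference depend on the scale on which the difference is taken, and challenge doses rise roughly threefold per step. The same fold improvement therefore gives very different milligram values in populations with different starting doses. The ANCOVA difference, raised as a power of 10, is a fold ratio; the Hodges-Lehmann value is in milligrams. The two cannot be set side by side.

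At stake is the only stated sensitivity check on the first-listed secondary endpoint. SAP practice elsewhere points the other way: immunological markers (8.2.3.1) and skin prick wheal (8.2.4.1) are log-transformed before modelling.

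**Working it through.** The plan has no figure to reproduce. The sample-size sections (Protocol 8.3, SAP 3.3) are blacked out, and no baseline CRD distribution, standard deviation, effect size or power is given for CRD.

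**1. Dose ladder** (Protocol 7.3.1.1.1 and 7.3.1.1.2, assuming no repeated or partial doses). Single doses of 1, 3, 10, 30, 100, 300, 1000, 2000 and 3000 mg accumulate to 1, 4, 14, 44, 144, 444, 1444, 3444 and 6444 mg. Baseline CRD can take the first six values.

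**2. One rung up from each baseline**

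| From → to (mg) | Change (mg) | Fold | log10 fold |
|---|---|---|---|
| 1 → 4 | 3 | 4.00 | 0.602 |
| 4 → 14 | 10 | 3.50 | 0.544 |
| 14 → 44 | 30 | 3.14 | 0.497 |
| 44 → 144 | 100 | 3.27 | 0.515 |
| 144 → 444 | 300 | 3.08 | 0.489 |
| 444 → 1444 | 1000 | 3.25 | 0.512 |

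**3. Hodges-Lehmann by hand.** The estimate is the median of (active change − placebo change) over all active-placebo pairs. Suppose placebo subjects do not change and every active subject rises one rung.

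- All start at 14 mg: 30 mg, or 0.497 on log10.
- All start at 144 mg: 300 mg, or 0.489.
- Equal numbers at all six baselines: (30 + 100)/2 = 65 mg, or (0.512 + 0.515)/2 = 0.51.

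**4. Hodges-Lehmann by simulation.** Assumptions, none from the documents: SD of log10 change 0.7, latent shift 0.42 log10, slope of Month 12 on baseline log CRD 1.0, and 3000 subjects per arm. The milligram estimates were 27 (baselines spread evenly), 30 (low), 100 (middle), 200 (high), 300 (mostly 144 or 444 mg) and 400 (all 144 or 444 mg). The range is 400/27, about 15-fold. The log10 estimate was 0.49 to 0.50, about 3.1-fold, throughout. Slopes of 0.8 and 0.6 gave 30 to 300 and 30 to 400 mg, so the pattern does not need a constant fold effect. Other assumed baseline mixes gave 20 to 143 mg against 0.49 to 0.50, and 13 to 230 mg against 0.41 to 0.45.

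**5. Power.** SAP 3.1 reports "198 were randomized in this study, 18 subjects in Part A and 180 subjects in Part B". Part B is 1:1:1:1 and Part A adds 4 per dose and 6 placebo: 180/4 + 4 = 49 per dose and 180/4 + 6 = 51 placebo. Under SAP 6.1.3, "all formal tests of hypotheses will be conducted at the two-sided level of significance with alpha=0.05". With the step 4 shift and SD, 30% adolescents and no missing data (assumed), 3000 trials per row gave power (%):

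| Baselines, slope | Wilcoxon, mg change | Wilcoxon, log10 change | log10 ANCOVA | Rank ANCOVA |
|---|---|---|---|---|
| Even, 1.0 | 70.0 | 79.5 | 80.9 | 78.7 |
| Even, 0.8 | 72.7 | 74.5 | 81.6 | 79.3 |
| Even, 0.6 | 73.5 | 67.4 | 82.4 | 80.7 |
| Middle, 1.0 | 74.4 | 79.0 | 81.5 | 78.7 |
| Middle, 0.8 | 74.8 | 76.5 | 81.2 | 78.3 |
| Middle, 0.6 | 75.8 | 74.0 | 82.3 | 80.0 |
| High, 1.0 | 75.4 | 79.3 | 81.5 | 78.9 |
| High, 0.8 | 77.5 | 79.6 | 83.1 | 80.4 |
| High, 0.6 | 76.2 | 73.9 | 81.6 | 79.2 |

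Log10-change ranking beats milligram ranking at slope 1.0, by about 2 points at 0.8, and loses at 0.6. Over a wider set of assumptions the difference ran from about 0 to +13 points at slope 1.0 and from about 0 to −14 at 0.6. Including slopes 0.9 and 0.7, the ANCOVA gained 5.5 to 10.9 points over the milligram Wilcoxon, and the rank ANCOVA 2.5 to 8.7. The gain vanished in some settings with all baselines at 144 or 444 mg. Type I error of the milligram Wilcoxon was 4.9 to 5.5%.

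**The case against.** The other side has a good deal in its favour.

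- Milligrams are the declared endpoint. Protocol 8.1.6.2 and SAP 4.2.1 list CRD and its change from baseline without transformation, and the responder rule has absolute thresholds of 144 and 1444 mg. A sensitivity analysis on another scale is a legitimate choice.
- Randomization makes baseline mixes comparable between arms, and the test is valid.
- The main ANCOVA already supplies a baseline-adjusted, fold-scale estimate.
- The Month 12 data were locked, unblinded and reported under SAP version 4.0 (SAP 11.1), so any new analysis is post hoc.

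All of this stands. It is why the milligram result should stay and why the point is minor. It does not make the milligram estimate comparable with the ANCOVA, or show which of the three changes caused a disagreement.

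A reader might infer more, and should not:

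- **That the test mostly ranks subjects by starting dose.** In simulation the rank correlation of milligram change with baseline was −0.25 to +0.26, and with log fold change 0.81 to 0.99.
- **That it forfeits 5 to 10 points of power against ranking log change.** That needs a nearly constant fold effect and widely spread baselines. The sign depends on regression to the mean, about which the documents say nothing.
- **That the responder definition favours fold change.** A move from 444 to 1444 mg is only 3.25-fold, yet it meets the second criterion.
- **That OL-300 is summarised only in milligram differences.** SAP 8.2.2.2 also counts subjects improved, stable or worse, and 8.2.1.2 applies the 10-fold rule to the same challenges.

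**Conclusion.** The point holds as a limited one. On the natural reading of SAP 8.2.2.1, the non-parametric analysis is on milligram change with no baseline CRD adjustment. Its Hodges-Lehmann estimate depends strongly on the baseline mix: about 15-fold across the assumed mixes for one fixed log10 shift. That follows from the ladder itself and held at all three slopes tried, although the exact milligram values rest on assumed baseline distributions and spread.

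Any power gain from switching to log10 change alone is conditional: small at slope 0.8, and absent or negative with stronger regression to the mean. Adjusting for baseline gave higher power in nearly all simulated scenarios. Type I error, the primary endpoint and the main CRD model are unaffected.

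**What to change.** 1. **Month 12, SAP 8.2.2.1.** Keep the existing result. Label it as a milligram-scale median of pairwise between-arm differences, not adjusted for baseline CRD. The label matters because this is not a difference in medians: 100 against 130 mg in the middle-baseline simulation.
2. **Add, marked post hoc:** the age-stratified Wilcoxon test and Hodges-Lehmann estimate on change in log10 CRD from Month 0, back-transformed to a fold difference with 95% confidence interval. This puts the estimate on the ANCOVA's scale.
3. **Preferably also add** a rank ANCOVA with baseline CRD and age group, so that a non-parametric check keeps the baseline adjustment.
4. **OL-300, SAP 8.2.2.2,** still written as future work: report geometric mean fold change beside the milligram change, for both baseline definitions.
5. **Leave SAP 12.4(f) as it is.** It records what was implemented.

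The cost is one rerun on existing Month 12 data and a few extra rows in the OL-300 tables. No data collection or decision already taken is affected.
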